### ***Randomization and blinding***

The biostatistician block-randomizes assignment of the ITT population to treatment (sham vs. active) using a 1:1 allocation ratio and, within each treatment group, stratification by sex (male/female) and non-opioid substance use disorder (presence/absence). The master codebook for randomization is kept in a secure location at Wayne State University and only the biostatistician and a research assistant (backup person) can access it.

Sham treatment, which controls for placebo effects, is designed to minimize sham recognition by the sponsor, principal investigator, participants, research assistants and treatment staff (i.e. quintuple blinding). Participants in the active arm receive standard NET treatment. Participants in the sham arm receive the same standard NET treatment as the active arm but will receive no electrical stimulation (cable is disabled beforehand). Sham credibility is evaluated for both arms based on surveys following the 1-hr treatment phase, and daily during device use. A single ‘treatment perception’ question asks: “How confident are you that you are receiving the real device treatment and not the placebo (sham) treatment?” Three ‘device satisfaction’ questions ask: (1) “How satisfied are you with the NET Device?” (2) “How willing are you to use the NET Model 901 Device?” and (3) “How willing are you to recommend the NET Model 901 Device to other people undergoing opioid discontinuation?”

Active and sham arms will receive identical device care and use instructions, identical equipment, attachment methods and locations, and identical daily reviews of device operation, electrode attachment, and withdrawal severity. The treatment apparatus presents both active- and sham-assigned participants with visual cues from the device’s “heartbeat” indicator (a blinking green light-emitting diode which indicates the device is active) during treatment. Research staff instruct each participant that the equipment is designed to be self-administered, that s/he can set the level of stimulation wherever it is comfortable, that stimulation is not always (and does not need to be) sensate, and that device use may be discontinued when s/he feels it is providing no benefit.

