During a given week, oral fluid samples and self/pharmacy reports that both indicate no illicit opioid, methadone, buprenorphine, or naltrexone use will be considered "opioid-abstinence without MOUD". Cumulative distribution function, time (days) to first use of illicit opioids, time (days) to first use of MOUD, and duration (weeks) of continuous abstinence without MOUD will be evaluated as supportive outcomes. Response profiles for each treatment arm are based on each participant's individual rates of weekly illicit opioid or MOUD use, including negative oral fluid results and daily

self (TLFB) of illicit opioid or MOUD use/non-use. **Table 1** presents explanatory cases of the primary efficacy endpoint measurement. The null hypothesis is that “opioid abstinence without MOUD” will not significantly differ between active and sham groups, whereas the alternative hypothesis is that “opioid abstinence without MOUD” will be superior in the active (relative to sham) treatment arm.

The secondary efficacy endpoint is each participant’s percentage of non-opioid drug-free weeks during the 12-week outpatient period. Non-opioids assessed include cocaine, sedatives, and stimulants. Use of alcohol and cannabis will be measured, but are not included in the secondary efficacy analysis, due to their legal status. Response profiles for each arm are based on each participant’s individual rates of weekly abstinence data, including negative oral fluid results and daily self-reports of non-opioid drug use/non-use (TLFB).

The secondary safety endpoint is the prevalence of all adverse events (AEs), serious adverse events (SAEs), adverse device effects (ADEs), serious adverse device effects (SADEs), unanticipated adverse device effects (UADEs), and device deficiencies.

Supportive and exploratory measures. Treatment retention will be measured throughout the inpatient and outpatient phases. Self-stimulation intensity (in 5-min bins), duration, and device on/off data from each NET Device are automatically transmitted to a computer server and processed offline. Opioid withdrawal symptoms, craving severity, and positive/negative affect are measured daily during the first inpatient week. Measures of depression, anxiety and stress, sleepiness, and health-related quality of life are obtained at the conclusion of inpatient and outpatient phases.

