Participant withdrawal. Participants can withdraw from the study at any time on request. Discontinuation of device use prior to completing the minimum 1-hr treatment period constitutes withdrawal from the study. The investigator may discontinue or withdraw a participant from the study for the following reasons: (1) significant study intervention non-compliance; (2) if any clinical adverse event (AE), laboratory abnormality, or other medical condition or situation occurs such that continued participation in the study is not in the best interest of the participant; (3) disease progression which requires discontinuation of the study intervention; (4) if the participant meets an exclusion criterion (either newly developed or not previously recognized) that precludes further study participation; or (5) participant is unable to receive treatment following enrollment.

Participants who sign the informed consent form and are randomized but do not receive the study intervention will be replaced. Participants who sign the informed consent form, are randomized, receive the study intervention, and subsequently withdraw or are withdrawn, will be replaced.

Participants who withdraw from the study will receive TAU as defined by treatment staff (who are independent of the research staff), where such care may include MOUD.

Lost to follow-up. A participant is considered lost to follow-up if s/he becomes unavailable for all video assessments following discharge from the inpatient environment.

Populations for analysis. The ITT analysis dataset and the safety analysis dataset will contain all randomized participants. The per-protocol analysis dataset will contain the subset of the ITT dataset who: (1) present with a COWS score of moderate or above; (2) receive at least 1 hr treatment from the device; and (3) complete at least one post-discharge video interview.

Efficacy endpoints. The primary analysis will assume that data came from a mixed-effect linear model. Each model will include a random intercept, fixed effect for treatment, participant-specific random effect and covariate corresponding to duration of inpatient residence. The primary hypothesis involves testing the main effect for treatment difference between the groups (sham vs. active). A likelihood ratio test will examine the group effect focusing on the primary hypothesis.

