Secondary endpoint analyses are not powered, but may be used to demonstrate additional benefits of the treatment, provided it has been demonstrated that the primary endpoint shows clear statistical significance, as well as clinical meaningful benefits of the treatment [19]. Analysis of the secondary endpoint resembles primary endpoint analysis, using mixed-effect model testing for the between-group main effect.

Given that participants can control the level of device stimulation, exploratory regression analyses will seek to identify potential relationships between device utilization (e.g. number of minutes device ‘on’ [non-zero intensity], average intensity while device ‘on’) and efficacy endpoints.

Expected outcomes. We selected a single primary outcome (abstinence without MOUD). From our past experience at this same treatment facility, the expected group means for sham and NET arms are 0.48 and 3.97 weeks of average opioid abstinence with standard deviations 1.19 and 3.46, respectively. This results in effect size of 1.12. This effect size based on pilot data is rather large,

which is often the case due to limited scope of the pilot study. Thus, we took a conservative approach as suggested by Kraemer et al. [20] with moderate effect size of 0.45.

Safety endpoints. Secondary safety endpoints (AEs, SAEs, ADEs, SADEs, UADEs and device deficiencies) will be summarized using descriptive statistics.

Subgroup analysis. The analysis will stratify by sex (male/female) and non-opioid SUD (presence/absence). The expected outcome is that allocation on those variables will be balanced between the two groups. It is not anticipated that the primary outcome (opioid abstinence without MOUD) will differ across these subgroups. If significant baseline group imbalance is detected on any variable and its correlation with outcome ( $\geq 0.30$ ), that variable will be included as a covariate in the inferential analyses. If systematic variation is noted by any subgroups for primary or secondary outcomes, further exploration will be conducted via cluster analysis.

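### Randomisation is stratified by sex and non-opioid SUD, but the primary and secondary efficacy models include neither factor: valid, but precision is forgone if the strata predict outcome

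*Combined protocol and SAP*

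**What the plan says.** Randomization and blinding describes 1:1 block randomisation with "stratification by sex (male/female) and non-opioid substance use disorder (presence/absence". Under Efficacy endpoints in the Statistical analysis plan, the model is specified as follows: "Each model will include a random intercept, fixed effect for treatment, participant-specific random effect and covariate corresponding to duration of inpatient residence". The test is also named: "A likelihood ratio test will examine the group effect focusing on the primary hypothesis". For the secondary endpoint the plan says: "Analysis of the secondary endpoint resembles primary endpoint analysis, using mixed-effect model testing for the between-group main effect".

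The two stratification factors return only under Subgroup analysis. That paragraph says "The analysis will stratify by sex (male/female) and non-opioid SUD (presence/absence", expects allocation to be balanced on both, and adds: "It is not anticipated that the primary outcome (opioid abstinence without MOUD) will differ across these subgroups". It then gives a conditional rule that begins "If significant baseline group imbalance is detected on any variable and its correlation with outcome" and sets a threshold of 0.30. A variable that meets both conditions becomes a covariate in the inferential analyses.

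**The concern.** Stratified allocation removes the strata from the treatment contrast. If the analysis leaves them out, the variance they explain stays in the error term. The standard error is then too large, the test tends to be conservative, and power is lost that the design has already paid for.

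The conditional rule does not repair this. It requires significant imbalance, which stratified blocks are there to prevent, so even a factor that passes the plan's own correlation threshold would stay out.

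The expectation of no difference across subgroups is stated for the primary outcome only. The secondary endpoint is each participant's "percentage of non-opioid drug-free weeks during the 12-week outpatient period", and one stratum is the presence or absence of non-opioid SUD. A link between the two is plausible, although the documents give no figure for it.

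**Working it through.** **Inputs from the documents.** N = 100 (50 per arm) and a standardised difference d = 0.45 after adjustment for duration of inpatient residence (Study design; Sample size determination). N = 125 appears under Missing data and serves as a sensitivity case. The correlation threshold of 0.30 gives R² = 0.30² = 0.09 for one factor and 2 × 0.09 = 0.18 for two uncorrelated factors.

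**Assumptions.** The documents state no alpha, sidedness, block size, stratum prevalence or R². I took two-sided 0.05, blocks of 4, prevalences of 40% and 60%, and R² of the two strata together = 0, 0.05, 0.09 and 0.18.

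**1. The plan's own figure.** The plan claims sufficient power without a percentage, so there is nothing to reproduce. By normal approximation, Φ(0.45 × √(100/4) − 1.96) = Φ(2.25 − 1.96) = Φ(0.29) = 61.4% two-sided. One-sided 0.05 gives 72.7%.

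**2. Closed form, two-sided, N = 100.** With the strata in the model, power is Φ(2.25/√(1−R²) − 1.96). Without them, under stratified allocation, power is Φ((2.25 − 1.96)/√(1−R²)) and size is 2[1 − Φ(1.96/√(1−R²))].

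| R² | Unadjusted power | Adjusted power | Gain (points) | Unadjusted size |
|---|---|---|---|---|
| 0.05 | 61.7% | 63.6% | 1.9 | 4.4% |
| 0.09 | 61.9% | 65.5% | 3.6 | 4.0% |
| 0.18 | 62.6% | 70.0% | 7.5 | 3.0% |

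**3. Simulation of the specified test.** There were 20,000 replicates per cell, with a Gaussian outcome at participant level and duration of stay in every model. One value per participant suffices because Table 1 scores missing weeks as non-abstinent, so everyone has 12 weeks. The likelihood ratio test (LRT) is N × log(RSS₀/RSS₁) against chi-square(1). The F-test has N−3 residual degrees of freedom unadjusted and N−5 adjusted.

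| R² | LRT power, without → with strata | Gain | F power, without → with strata | Gain | LRT size, without → with strata |
|---|---|---|---|---|---|
| 0 | 61.0 → 61.8% | +0.8 | 59.6 → 59.6% | 0 | 5.3 → 5.5% |
| 0.05 | 61.8 → 64.5% | +2.7 | 60.5 → 62.5% | +2.0 | 4.9 → 5.8% |
| 0.09 | 61.6 → 65.8% | +4.2 | 60.2 → 63.7% | +3.5 | 4.7 → 6.0% |
| 0.18 | 62.1 → 70.3% | +8.2 | 60.6 → 68.3% | +7.7 | 3.7 → 6.0% |

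Monte Carlo standard errors are about 0.35 points for power and 0.15 for size. With blocks of 4 or 8 and prevalences of 40/60% or 30/80%, the LRT gain at R² = 0.05 / 0.09 / 0.18 ranged over 2.5–3.0 / 3.8–4.5 / 7.7–8.8 points. With only non-opioid SUD prognostic, it was 2.7 / 4.2 / 8.0. At N = 125 it was 2.2 / 3.4 / 6.9, and 0.5 at R² = 0.

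**4. Precision.** Unadjusted confidence intervals were wider by factors of 1.025, 1.048 and 1.105. Since 100/1.025² = 95, 100/1.048² = 91 and 100/1.105² = 82, the unadjusted analysis of 100 participants is as precise as an adjusted analysis of about 95, 91 and 82.

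**5. The imbalance rule.** A 5% test of imbalance on either factor fired in 0 of 680,000 simulated trials. The reason is structural. With blocks of 4, each stratum can be off by at most 2, so a factor level (two strata) by at most 4. At 20% prevalence that is 12 against 8 of 50 per arm: z = 0.08/√(2 × 0.2 × 0.8/50) = 1.0, p = 0.317. Only an extreme case, blocks of 8 with 20% prevalence and the worst possible draw (14 against 6), reaches p = 0.046.

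**6. Secondary endpoint, illustration only.** For an assumed difference D in percentage of drug-free weeks between participants with and without non-opioid SUD, R² = p(1−p)D² / [p(1−p)D² + SD²]. Take prevalence p from 40 to 80% and within-group SD from 30 to 40 points:

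- D = 10 gives 16/1616 = 0.01 to 25/925 = 0.03.
- D = 20 gives 64/1664 = 0.04 to 100/1000 = 0.10.
- D = 30 gives 144/1744 = 0.08 to 225/1125 = 0.20.

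The lower ends use p = 80% and SD 40; the upper ends use p = 50% and SD 30.

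**The case against.** The list under Efficacy endpoints says what each model will include, not that the list is complete. Study design treats duration of device exposure as a covariate, and that is not listed either. The sentence about stratifying the analysis could be read as covering the primary analysis, since its paragraph also discusses the primary outcome and the inferential models. This shows that the text is not fully clear, but it does not put the strata in the model. The sentence stands under Subgroup analysis, and the conditional rule would be redundant for these two factors if they were already included.

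On the plan's own premise the primary analysis loses nothing, and every non-zero R² above is assumed. That stands.

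The size also depends on sidedness. The alternative hypothesis is directional, and at one-sided 0.05 the closed-form gains at N = 100 are about 1.4 / 2.5 / 5.2 points. At the pilot effect of 1.12, power is already 99.98% and nothing is gained, but the plan deliberately powers on 0.45.

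The sharpest point is that adding the strata to the LRT moves its size slightly above nominal (5.5 to 6.0%), so part of the LRT gain is bought with size. The F-test gains of 2.0 / 3.5 / 7.7 points are the cleaner measure. If both things change at once, adjusted F against the planned unadjusted LRT, power moves by −1.4 / +0.7 / +2.1 / +6.2 points at R² = 0 / 0.05 / 0.09 / 0.18. The negative value at R² = 0 comes from the change of reference distribution, not from the adjustment.

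Finally, the secondary analysis is unpowered and depends on primary success, so little rests on it.

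**Conclusion.** The concern holds as a point about efficiency, to be considered rather than required. On an ordinary reading, neither efficacy model contains the stratification factors, and the conditional rule will practically never bring them in. A positive result from the planned test remains valid: its size is close to nominal at small R² and conservative at 0.18 (3.7%).

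At N = 100, d = 0.45 and two-sided 0.05, the like-for-like power forgone is about 2 to 3 points at R² = 0.05, 4 at 0.09 and 8 at 0.18. It is essentially zero if the strata do not predict outcome. R², alpha, sidedness, block size and prevalences are all assumptions. With power near 61% on these inputs, a few points that need no extra participants are worth having.

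**What to change.** Under Efficacy endpoints, state that the primary and secondary models include sex and non-opioid SUD, as recorded for randomisation, as fixed covariates alongside treatment and duration of inpatient residence, whatever the observed balance. Under Subgroup analysis, reword the sentence about stratifying so that it agrees, and limit the conditional rule to other baseline variables.

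The cost is one added sentence, one reworded sentence and 2 degrees of freedom. Both factors are already collected; a footnote to the Schedule of Activities describes a wider drug screen for this purpose.

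Optional and separate: use an F or t reference instead of the LRT chi-square. For the adjusted model this brings size from 5.5–6.0% to 4.9–5.3%, at a cost of about 2 points of nominal power. It is not part of the gain from adjustment.

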### ***Outcome measures***

During the 12-week outpatient period, participants will be interviewed for safety and efficacy endpoints and undergo a remote drug screen. Remote interviews reduce risk of COVID-19 exposure for the participant and research assistant, and decrease transportation barriers (increased feasibility). Each week, the research assistant hosts a live video call with the participant, and conducts a timeline follow-back (TLFB) review of opioid, MOUD, stimulant, sedative, cannabis and alcohol use for each of the prior 7 days. At discharge from the inpatient facility, each participant will be given 12 kits (plus

one spare) of the Premier Biotech OralTox OT-80605, an FDA 510(K) cleared 6-panel rapid oral fluid drug screen. Each test covers amphetamines and methamphetamine (positive cutoffs = 50 ng/ml), opioids and THC (positive cutoffs = 40 ng/ml), oxycodone and cocaine (positive cutoffs = 20 ng/ml). Each individually packaged test is sealed in foil and is marked with a lot number and expiration date. Each individual test contains a QR code that encodes a unique identification number that will be used to validate authenticity and uniqueness of the screen. The participant receives printed and verbal instructions for use from the research assistant, is observed during each test, and test results with authenticating QR code are captured as an image file by the research assistant and saved for validation. In order to conduct this FDA-qualifying study during the COVID-19 pandemic, remote test methods were evaluated for use during the outpatient phase. When this study began, FDA had only approved a limited selection of oral fluid rapid tests for use in research. The authors selected TLFB self-report as the primary source for data, supplemented by such relevant oral fluid tests as were FDA approved.

The primary efficacy endpoint is each participant's overall percentage of weekly abstinence from illicit opioid use without use of MOUD. This is defined as the percentage of each participant's negative oral fluid samples and self-reports of illicit opioid, methadone, buprenorphine, and naltrexone use per week throughout the 12-week outpatient study period. The rationale for choosing this endpoint is to perform a rigorous test of the isolated efficacy of NET, with the safety net of allowing (and measuring) participants' use of MOUDs.

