h = illicit opioid (e.g., heroin) drug screen or self-report is positivem = medication for opioid use disorder (MOUD) or self-report is positive

'-' = missing value

Cases measuring “abstinence without MOUD”:

Heroin use, no MOUD {1,1,1,h,h,1,1,1,1,1,h} = 9/12

Heroin use, no MOUD, missing weeks {1,1,1,h,h,1,--,1,1,--,} = 6/12

MOUD use, no Heroin {1,1,m,m,m,m,1,1,1,1,1} = 8/12

MOUD use, no Heroin, missing weeks {1,1,m,m,m,m,1,1,--,} = 4/12

[figure not shown]
Heroin use, MOUD use {1,1,h,h,h+m,m,m,m,m,h,1,1} = 4/12

Heroin use, MOUD use, missing weeks {1,1,h,h,h+m,m,--,m,h,--,} = 2/12

[figure not shown]
**Table 2.** Participant selection criteria

Inclusion Criteria	Exclusion Criteria

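### The primary mixed model lists two random terms that the endpoint, one percentage per participant, cannot separate; the treatment estimate is safe, but the model needs to be pinned down

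*Combined protocol and SAP*

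**What the plan says.** Under Outcome measures, the primary endpoint is each participant's "overall percentage of weekly abstinence from illicit opioid use without use of MOUD" over the 12 outpatient weeks. Table 1 scores it as a single fraction per participant; for example, the case labelled "MOUD use, no Heroin, missing weeks" gives 4/12. Missing weeks count as not abstinent, so every participant has a denominator of 12.

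Under Efficacy endpoints in the Statistical analysis plan: "The primary analysis will assume that data came from a mixed-effect linear model". The terms follow: "Each model will include a random intercept, fixed effect for treatment, participant-specific random effect and covariate corresponding to duration of inpatient residence". The test is then named: "A likelihood ratio test will examine the group effect focusing on the primary hypothesis".

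One phrase under Outcome measures points to weekly data, because response profiles are based on "individual rates of weekly illicit opioid or MOUD use, including negative oral fluid results and daily" self-report. The plan does not say whether the model takes the summary percentage or the 12 weekly results. It lists no time term and names no grouping for the random intercept, and the trial has a single site. It states no alpha, no choice between maximum likelihood and REML, and no reference distribution for the test. The randomisation strata (sex, non-opioid substance use disorder) are not in the listed model; the Subgroup analysis paragraph says only that the analysis will stratify by them.

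**The concern.** A random effect for a participant is informative only if that participant contributes more than one observation. The endpoint as defined contributes one. Two random terms at participant level are then one too many even for weekly data, and two too many for the summary percentage.

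This is the trial's single confirmatory test, and the secondary endpoint may be used only if the "primary endpoint shows clear statistical significance". A model without a unique fit leaves the analyst to decide which terms to drop, which unit to analyse and which reference distribution to use. Those decisions should be on paper before unblinding.

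**Working it through.** The plan gives no type I error, alpha or variance components for this model, so it has no figure of its own to reproduce. The inputs are the endpoint definition (one x/12 per participant), the listed model terms, N=100 (50 per arm), the alternative N=125 in the Missing data paragraph, and the pilot means and SDs. Two-sided alpha of 0.05 is an assumption.

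**1. One percentage per participant.** Let a be the variance of the random intercept, b that of the participant effect and e the residual variance. Each observation has variance a + b + e and is independent of the others, so the likelihood depends only on that sum. In a test data set the log-likelihood was -141.057 for every split tried. A fit with a single participant term converged on an arbitrary even split (0.426 and 0.426), with a treatment coefficient of 0.0354, identical to ordinary least squares. Another such fit returned a non-positive-definite Hessian.

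**2. Twelve weekly values per participant.** The between-participant part of the likelihood depends on e + 12(a + b) and the within-participant part on e. So e and the sum a + b can be estimated, but a and b cannot be told apart: the log-likelihood was -679.102 for (a, b) = (0.25, 0), (0.125, 0.125) and (0, 0.25). One participant intercept is enough.

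**3. Size of the test if a chi-square cut-off is used.** In a normal linear model with p mean parameters, the maximum-likelihood ratio statistic is N·ln(1 + F/(N - p)). Rejecting above 3.841 is the same as rejecting when F > (N - p)(exp(3.841/N) - 1). Here p = 3 (intercept, treatment, inpatient duration).

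- N=100: 97 × (exp(0.03841) - 1) = 97 × 0.03916 = 3.799, against the exact 5% point of F(1, 97), 3.939. Size = P(F(1, 97) > 3.799) = 5.42%.
- N=125: 122 × (exp(0.03073) - 1) = 122 × 0.03121 = 3.807, against 3.919. Size = 5.33%.

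Simulations under no treatment effect, with outcomes matched to each arm's pilot mean and SD:

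| Data | Chi-square cut-off | F reference |
|---|---|---|
| x/12 per participant, N=100 | 5.2% to 5.4% | 4.8% to 5.0% |
| x/12 per participant, N=125 | 5.1% to 5.3% | 4.7% to 5.0% |
| 12 weekly values, one participant intercept, N=100 or 125 | 4.6% to 5.5% | not run |

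The first two rows use 100,000 trials per scenario. The third uses 20,000, with a simulation standard error of 0.15 points.

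**4. Leaving the strata out.** Randomisation is stratified, so an analysis that ignores strata related to outcome overstates the standard error. If the strata explain an assumed 15% of the variance, the unadjusted t statistic must pass 1.984/√0.85 = 2.152 on its true scale, which gives a size of about 3.4%. Simulation gave 3.4% unadjusted and 5.0% adjusted. This error is conservative, and its size depends wholly on the assumed 15%.

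**The case against.** The strongest defence is that the two phrases may be a loose way of naming one participant-level term in a weekly model. The weekly wording under Outcome measures and the mixed-effect additive model used for the power simulation allow that reading. One intercept is then identifiable, the data are balanced because missing weeks are scored, and the test is close to nominal. This stands as a plausible intention. It does not remove the need to write the intention down, because the endpoint definition and Table 1 point to the summary percentage.

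A reader might also infer several stronger things that the documents do not support.

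- *That non-identifiability inflates the error rate.* It does not. Only the split of the variance is undetermined; the treatment estimate and its likelihood are unchanged.
- *That the plan specifies a chi-square test.* It says only that a likelihood ratio test will be used. The 5.4% and 5.3% apply to an assumed procedure.
- *That unequal variances make the test too liberal.* The pilot figures come "with standard deviations 1.19 and 3.46, respectively", a variance ratio of (3.46/1.19)² = 8.5. With the planned 50 per arm, the pooled and true standard errors are both √(1.19²/50 + 3.46²/50) = 0.517. An imbalance would be an assumption, and its direction decides the result: the pooled standard error is 7.7% too small at 55 sham and 45 active, but 8.3% too large at 45 and 55. These SDs also go with very different means (0.48 and 3.97 weeks), so they describe the alternative. If treatment has no effect, the arms share one distribution.
- *That the error rate could be gross.* Weekly data analysed with no participant effect gave 26% to 47% in simulation, but the plan includes such an effect.

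**Conclusion.** The point holds as a specification defect in the primary analysis. On the endpoint as defined, the three variance terms cannot be separated; on a weekly reading, the two random terms duplicate each other. No reading of the listed model makes both estimable. The plan therefore leaves the analyst to choose the unit, the retained term, the estimation method and the reference distribution.

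The numerical consequence is small. The treatment estimate does not change. The excess type I error is about 0.3 to 0.4 percentage points for normal data, given maximum likelihood, a chi-square cut-off, two-sided alpha of 0.05 and three mean parameters. It is no larger for pilot-like percentages and absent in some weekly scenarios. The case for a change rests on fixing the confirmatory analysis in advance, not on a material bias. It should be settled before unblinding.

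**What to change.** Replace the model paragraph with a statement that the primary analysis is one linear regression (ANCOVA) of each participant's percentage on treatment and the randomisation strata (sex, non-opioid substance use disorder). State alpha and sidedness, and test the treatment coefficient against a t or F distribution with residual degrees of freedom. Robust (HC3) standard errors, or a permutation test stratified as randomised, are optional sensitivity checks. If the sponsor prefers a weekly model, it should name a single participant intercept and a small-sample degrees-of-freedom method.

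The sponsor must also say how duration of inpatient residence is handled. The sample size paragraph defines the powered effect after adjustment for it, so it cannot be dropped or kept without comment. It is also known only at discharge, after randomisation.

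The cost is SAP wording, a check that the power statement still matches the model, and a p-value reference that is very slightly less favourable (at N=100 with three mean parameters, an F cut-off of 3.939 in place of an effective 3.799). No data collection changes.
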